#### **15. Withdrawal of Participants**

Individuals may withdrawal from the study at any point by emailing the PI or study coordinator. A patient may also be withdrawn/removed by the study team, if necessary, to protect the patient's health. Once a patient withdraws, the reason will be documented.

#### **16. Risk to Participants**

We anticipate inconveniencing some participants due to the lengthened provider-patient interaction during the enrollment, LCS intervention, and subsequent surveying process. Some participants may find questions on surveys related to family history of substance use or their own substance use uncomfortable and may skip questions at any point. There is a minor risk of loss of privacy or breach of confidentiality. To address the risk for loss of confidentiality associated with conducting research and collecting data, rigorous procedures will be in place to ensure the security and confidentiality of the dataset during analyses. As noted previously, all data will be coded when stored on a secure Emory University server using Redcap. Access to the data will be limited to the study PI, co-investigators, approved research personnel. The PI and collaborators have completed in depth online and in-person training in human subjects training at Emory University. Participants may find the wearable devices uncomfortable and will be educated on how to properly wear them and check for as well as prevent skin irritation (e.g., taking off to shower or if wet allowing band to dry or use replacement band).

#### **17. Potential Benefits to Participants**

We anticipate that those participants randomized to the LCS interventions will have decreased pain scores and improved functioning.

#### **18. Compensation to Participants**

Participants will receive a \$50 clinical gift card, reloadable card, upon finishing baseline study visit and upon study completion and returning study equipment for a total of \$100. Additionally, the team will reimburse those needing assistance to attend study visits up to \$20 via gift card if they cannot secure personal or public transportation to attend sessions.

#### **19. Data Analysis, Management and Confidentiality**

**Protocol Title:** Implementing and Evaluating the Effect of Personalized Pain Coaches After Orthopaedic Surgery for Patients with Sports Medicine Injuries to Improve Postoperative Outcomes

---

Descriptive statistics will be used to examine the sample's characteristics and demographics (e.g., means, frequencies). Paired t-tests will be used to examine changes within participants from pre- to post-surgery. Mixed effects modeling will be used to examine mean change in outcomes over time and based on demographics as well as differences between those who do and do not work with the LCs while wearable devices are collecting data. Surveys will be coded with study participant ID numbers. All hard copies will be stored in locked filing cabinets in the PI's office. Paper survey data will be entered into RedCap. A master list of study ID # and names with emails of participants will be stored on Emory servers and only accessible to the PI and the coordinator.

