## 1. Study Summary

Study Title	Implementing and Evaluating the Effect of Personalized Pain Coaches After Orthopaedic Surgery for Patients with Sports Medicine Injuries to Improve Postoperative Outcomes
Study Design	Three arm randomized control trial
Primary Objective	The objective of this randomized controlled trial is to examine how the integration of a trained Life Care Specialist improves postoperative recovery related to patient-reported pain outcomes following orthopaedic injury
Secondary Objective(s)	Examine how the integration of a trained Life Care Specialist improves postoperative recovery related to opioid utilization and objective functional outcomes following orthopaedic injury
Research Intervention(s)/Interactions	The LCS will work with the patient to create a pain management plan focused on behavioral education. The LCS interventions can encompass all, but not limited to, the information included below: 

• Opioid Risk Education

• Therapeutic Intervention

• Clinical Pain Coordination

Study Population	Orthopaedic patients seen at Emory and Grady
Sample Size	150
Study Duration for individual participants	~90 days
Study Specific Abbreviations/ Definitions	LCS, Life care specialist
Funding Source (if any)	National Football League (NFL)

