## 2. Objectives

**Protocol Title:** Implementing and Evaluating the Effect of Personalized Pain Coaches After Orthopaedic Surgery for Patients with Sports Medicine Injuries to Improve Postoperative Outcomes

---

The *objective* of this randomized controlled trial is to examine how the integration of a trained Life Care Specialist improves postoperative recovery related to patient-reported pain outcomes, opioid utilization, and objective functional outcomes following orthopaedic injury.

**Aim 1:** Examine differences in post-surgical patient-reported pain related outcomes and opioid utilization between participants in the intervention arms compared to those in the control arm.

*Hypothesis 1.1:* Those randomized to the intervention arms will report improved average patient-reported pain related outcomes compared to participants in the control, standard of care, arm.

*Hypothesis 1.2:* Participants in the intervention arms will have decreased utilization of opioid pain medications both in the inpatient and outpatient setting.

**Aim 2:** Compare postoperative functional outcomes among intervention and control groups during their hospitalization and postoperatively.

*Hypothesis 2:* Objective functional outcomes captured from actigraphy devices will indicate improved physical functioning among those in the intervention arms compared to participants in the control arm.

**Aim 3:** Evaluate patient-reported pain related outcomes and opioid utilization between participants randomized to the in-person intervention and the telehealth delivered intervention arms.

*Hypothesis 3:* Improvements in patient-reported outcomes and opioid utilization will be similar across study arm groups, thereby indicating the utility of delivering the intervention both in person or remotely to improve care outcomes.

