#### **4. Study Endpoints**

During the conduct of this study, assessments will occur one month to one week prior to surgery, 2 weeks, 6 weeks, and 3 months postoperatively. Study measures at these points will assess patient-reported outcomes using surveys, opioid consumption using both electronic health records and remote monitoring, and functioning using wearable actigraphy devices.

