## **6. Procedures Involved**

If the patient meets inclusion criteria, the CRC will visit patient during their preoperative consult or call the referred patient through his/her number listed on Epic. If unable to visit in person and reach through call, the CRC will message patient through the Secure Chat feature on Epic to potentially schedule an e-consent. If informed consent is obtained, they will be enrolled into REDCap for randomization into one of the three groups. A simple number generator, within RedCap, will sequentially randomize participants into control or one of the two intervention arms. After consenting, enrolling, and allocation, research staff will administer a battery of measures on tablets stored in REDCap, or on paper and later transcribed into REDCap to all participants. In the event the participant is unable to complete study measures during the clinic visit they will be emailed a secure link to RedCap to complete the consent form and the study measures.

Those randomized to the intervention will either meet with a Life Care Specialist for 1 hour before surgery, either in person or via Zoom® during their preoperative consult or at another time no later than 24 hours before surgery.

During their follow up visits with the surgical team at Grady Hospital or Emory Orthopaedics scheduled at 2-weeks, 6-weeks, and 3-months postoperatively participants will again be provided a tablet to complete outcome measures. In the event participants cannot physically travel to the clinic, appointments will be conducted over video conferencing and participants will have the option to be emailed the outcome measures to complete. If they are unable to complete the measures via email within 72-hours study staff will call participants to complete measures over the phone. If no response, paper copies of the measures will be mailed to participants with prepaid

**Protocol Title:** Implementing and Evaluating the Effect of Personalized Pain Coaches After Orthopaedic Surgery for Patients with Sports Medicine Injuries to Improve Postoperative Outcomes

---

postage to return them or QR code post cards to complete surveys. There is a one week window for the first follow up visit, two week window to complete measures for the second follow up study visit, and four weeks for the last study visit. Study staff will call participants and offer to video conference with them within 48 hours of surgery to review how to wear the actigraphy device and use the MEMS cap.

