#### **10. Inclusion and Exclusion Criteria**

We will recruit 150 participants from the orthopaedic sports medicine service at Grady and Emory Healthcare for this study. Individuals between 15–45 years old, scheduled for orthopaedic surgery due to sports medicine injuries (e.g., anterior cruciate ligament tears, meniscus injury, rotator cuff injury, etc.), and those who are actively employed or full-time athletes prior to injury will be eligible. Individuals unable to provide consent, those undergoing revision procedures, individuals without access to an internet connected device, and individuals who are unemployed or retired at time of injury will be ineligible. No one will be excluded from participation based on gender, race, or ethnicity. Individuals who are incarcerated or pregnant will not be eligible. Individuals unable to consent and those unable to communicate in English will be excluded since all surveys are validated in English.

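### Section 19 tests pre-post change within participants and models mean change with no stated baseline adjustment; for outcomes with a pre-surgery score, the arm comparison should be baseline-adjusted

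*Combined protocol and SAP*

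**What the plan says.** Section 1 describes a "Three arm randomized control trial", and Section 10 sets the size: "We will recruit 150 participants from the orthopaedic sports medicine service at Grady and Emory Healthcare for this study". Aim 1 in Section 2 is a between-arm question: "Examine differences in post-surgical patient-reported pain related outcomes and opioid utilization between participants in the intervention arms compared to those in the control arm". Section 4 provides one pre-surgery and three postoperative measurements: "assessments will occur one month to one week prior to surgery, 2 weeks, 6 weeks, and 3 months postoperatively".

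The analysis plan is a few sentences in Section 19. Besides descriptive statistics it names two methods:

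- The first is a comparison of each participant with himself or herself: "Paired t-tests will be used to examine changes within participants from pre- to post-surgery".
- The second is a longitudinal model, described in these words: "Mixed effects modeling will be used to examine mean change in outcomes over time and based on demographics". The same model is also meant to cover a group comparison, namely "differences between those who do and do not work with the LCs while wearable devices are collecting data".

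It mentions no baseline covariate, common-baseline constraint or arm-by-visit term. The only between-group wording is tied to the wearable period, which Section 6 ends at the 2-week visit at the latest. Read literally, the 6-week and 3-month survey scores have no stated arm comparison.

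On timing, Section 6 has staff give the measures once consent, enrolment and allocation are complete. Section 9 places the intervention meeting in the same preoperative visit as the baseline surveys.

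**The concern.** All participants have surgery. A paired test from before to after surgery therefore measures the course of recovery, whichever arm it is run in, and cannot answer Aim 1.

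The mixed model is the only route to the arm effect, but its wording leaves open how the baseline score is used. One common way to model mean change puts baseline in as an outcome row with a free mean for each arm. With complete data, the arm-by-visit contrast is then the difference between arms in change from baseline. Because surgery intervenes, pre- and postoperative scores may correlate only weakly, and in that case a change score is an imprecise way to use the baseline.

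With 150 participants in three arms, precision is scarce. A more precise analysis of the same data is available, and the present wording does not secure it.

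**Working it through.** **The plan's own figure.** The 150 cannot be reproduced, because no alpha, power, effect size, SD or dropout is given. Unrelated assumption sets land close to it: a two-sided 0.05 test with 80% power and a standardised difference of 0.56 needs 3 × 51 = 153; a difference of 0.60 with 10% dropout gives 147. The 150 is neither confirmed nor refuted, and this point does not depend on how it was reached.

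**Inputs.** From the documents: 150 participants, three arms, one baseline and three follow-ups. Assumed: equal allocation (Section 6 says only "A simple number generator, within RedCap, will sequentially randomize participants into control or one of the two intervention arms"), no dropout, equal SDs before and after surgery, two-sided 0.05, 80% power, and a baseline-to-follow-up correlation r of 0.2 to 0.7. The SD of 10 is the PROMIS population norm quoted in Section 6, not a trial SD.

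**Variance for one follow-up, relative to a single score.**

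- Follow-up score alone: 1
- Change score: 2(1 − r)
- Baseline-adjusted: 1 − r²
- Adjusted ÷ change: (1 − r²) / [2(1 − r)] = (1 + r)/2

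The detectable difference for both intervention arms against control (100 v 50) is 2.8 × 10 × √(variance factor) × √(1/100 + 1/50).

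| Assumed r | Change variance | Adjusted variance | Ratio | Detectable, change | Detectable, adjusted |
|---|---|---|---|---|---|
| 0.2 | 1.60 | 0.96 | 0.60 | 6.13 | 4.75 |
| 0.3 | 1.40 | 0.91 | 0.65 | 5.74 | 4.63 |
| 0.5 | 1.00 | 0.75 | 0.75 | 4.85 | 4.20 |
| 0.6 | 0.80 | 0.64 | 0.80 | 4.34 | 3.88 |
| 0.7 | 0.60 | 0.51 | 0.85 | 3.76 | 3.46 |

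A simulation with 50 per arm and 20,000 runs gave adjusted-to-change ratios of 0.65 at r = 0.3 and 0.76 at r = 0.5, against 0.65 and 0.75 in theory.

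**Precision at a fixed 150.** Against a change-score analysis, adjustment is worth 150/0.60 = 250, 150/0.75 = 200 or 150/0.85 ≈ 176 participants at r = 0.2, 0.5 or 0.7.

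**Three follow-ups.** The single-follow-up figures are not exact for a model using all three visits. For the mean of three follow-ups with every pairwise correlation equal to r, the variances are p = (1 + 2r)/3 for follow-up alone, p + 1 − 2r for change, and p − r² adjusted. At r = 0.5 these are 0.667, 0.667 and 0.417, a reduction of 37.5% against change. At r = 0.2 and 0.7 the reductions are 60% and 22.5%. One common correlation is itself an assumption, and surgery makes it doubtful.

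**Which outcomes qualify.** The PROMIS scales have a pre-surgery score. Actigraphy has a pre-surgery week, but it is a clean baseline only if that week precedes the LCS session. No same-scale pre-surgery value is described for inpatient opioid dose per day, inpatient pain ratings or opioid use recorded by the bottle cap.

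**Baseline after allocation.** If knowing the allocation, or the LCS session itself, shifts the baseline in the intervention arms by δ, a change-score comparison is biased by δ and an adjusted one by about rδ. Adjustment is less exposed but not immune.

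**The case against.** The strongest reply is that Section 19 does not commit to change scores. Modelling mean change over time is ordinary language for a longitudinal model, and one with a common baseline mean fits the text and is already efficient. This stands: the change-score comparator is a reading the text permits, not one it fixes, and against a constrained model the gain is about zero.

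It can also be said that the paired t-tests are assigned only to within-participant change. That is true, and nothing in Section 19 presents them as evidence of efficacy. Reading significant tests in the intervention arms that way would be a reader's mistake, which the plan can forestall.

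Some stronger readings are tempting and are not supported:

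- **That the trial could be run with 20–40% fewer patients.** That range needs r between 0.2 and 0.6, a single follow-up and a change-score comparator. None of these is fixed by the documents, and 150 is the stated target.
- **That the baseline is wasted.** Paired tests and change analyses do use it. What is missing is a statement of how it enters the arm contrast.
- **That change scores always add noise.** Against the follow-up score alone this holds only for r below 0.5. At r = 0.6 the change variance is 0.80, below 1.
- **That the gain covers all of Aim 1.** The opioid-dose outcomes have no matching baseline.
- **That only wording needs to change.** The order of assessment and allocation in Section 6 must change too.

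**Conclusion.** The point holds as a recommendation the plan should adopt. Section 19 names one method that does not compare arms and one whose treatment of baseline is left open, although a baseline is collected. Baseline adjustment is in large samples at least as precise as either the change score or the follow-up score alone, since 1 − r² exceeds neither 2(1 − r) nor 1.

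For one follow-up with equal SDs, its variance is 40%, 25% or 15% below that of a change-score analysis at assumed r of 0.2, 0.5 or 0.7. Detectable differences are correspondingly about 23%, 13% or 8% smaller (1 − √0.60, 1 − √0.75, 1 − √0.85). These figures rest on an r and a comparator that the documents do not settle. The advantage is confined to the PROMIS scales and, conditionally, actigraphy.

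**What to change.** In Section 19:

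- Report pre- and post-surgery means by arm descriptively, and drop the paired t-tests as inferential tests.
- For each PROMIS scale, fit the mixed model to the 2-week, 6-week and 3-month scores with the baseline score as a covariate, or fit a constrained longitudinal model with a common baseline mean. Take the LCS effect from the arm and arm-by-visit terms.
- Treat actigraphy in the same way, up to the 2-week visit only, and only where its pre-surgery week precedes the LCS session.
- State that outcomes without a same-scale pre-surgery value are compared between arms without this adjustment.

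In Sections 6 and 9, move the baseline battery before allocation, or at least before the LCS session. A common baseline mean is justified by randomisation only if the baseline precedes allocation. For participants already enrolled, state the post-allocation timing as a limitation.

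The cost is small: revised analysis text and one reordered step, with no extra patients, visits or instruments. The reordering cannot be applied retrospectively.

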- Actigraphy based sleep and activity data (e.g. average hours of sleep, average daily steps): Study participants will be provided with a wrist actigraphy device to wear during a week before their hospitalization and throughout their recovery until their 2-week follow up appointment with the surgical team or until the watch battery loses its charge, whichever occurs first. Participants will return their actigraphy devices at the 2-week follow up appointment or be provided a pre-paid envelope to take home and mail back the device after the visit. Wrist actigraphy is a valid and objective tool to measure activity patterns and sleep-related parameters, which has been used in patient populations with both acute and chronic pain.(An et al., 2020; Smith et al., 2018) Actigraphy data includes objective quantitative measures of sleep, such as total sleep time, sleep latency, fragmentation, wake after sleep onset, and sleep efficiency. Additionally, activity level is also captured using wrist actigraphy, including total activity time, steps, physical activity intensity, and total energy expenditure. Participants will receive, and be trained on how to wear, a screen-less actigraphy device on their wrist (GT3XP-BTLE, Actigraph, LLC, USA). Devices will be set to record in 30-second epochs at a medium sensitivity level for scoring sleep and wake time. Wear time validation will be accomplished using the Choi algorithm, as it more accurately estimates time worn accounting for forward and backward motions.(Choi et al., 2011) The sleep data will be computed using the Cole-Kripke algorithm, which accurately distinguishes sleep from wakefulness approximately 88% of the time.(Cole et al., 1992) Metabolic equivalent of tasks and energy expenditure will be measured with the Freedson algorithms.(Freedson et al., 1998) By uniquely pairing actigraphy data with PROMIS patient-reported pain, sleep, and physical function measures, this study will be one of the first to provide a robust analysis of sleep quality and activity in tandem to pain presentations in adult surgical patient populations during hospitalization and throughout immediate post-discharge recovery following surgery. These research efforts adhere to recommended best practices for using actigraphy to examine health outcomes.(Berger et al., 2008)

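### Section 19's only between-group wording does not specify the as-randomised, three-arm comparisons of Aims 1 to 3, nor any arm comparison at 6 weeks or 3 months

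*Combined protocol and SAP*

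**What the plan says.** Section 19 (Data Analysis, Management and Confidentiality) names three analyses.

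- Descriptive statistics for the sample.
- A within-participant test: "Paired t-tests will be used to examine changes within participants from pre- to post-surgery".
- A mixed model, described in two parts. The first is longitudinal: "Mixed effects modeling will be used to examine mean change in outcomes over time and based on demographics". The second is the only between-group statement in the section: "differences between those who do and do not work with the LCs while wearable devices are collecting data".

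Section 19 does not mention randomised arm, an analysis population, an arm-by-time term or any contrast among three arms.

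The objectives in Section 2 are framed by arm. Aim 1 looks for differences "between participants in the intervention arms compared to those in the control arm". Hypothesis 1.1 reads: "Those randomized to the intervention arms will report improved average patient-reported pain related outcomes". Aim 2 compares function between intervention and control groups, and Aim 3 compares the in-person arm with the telehealth arm, as randomised.

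On timing, Section 4 says that "assessments will occur one month to one week prior to surgery, 2 weeks, 6 weeks, and 3 months postoperatively". Section 6 has the actigraphy watch worn for a week before hospitalization and then "throughout their recovery until their 2-week follow up appointment with the surgical team or until the watch battery loses its charge, whichever occurs first".

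**The concern.** Anyone who follows the between-group clause as written meets three mismatches with Section 2.

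1. **Grouping.** Working with the LCS happens after randomisation. Section 6 allocates participants first, and the LCS session may then be held at the preoperative consult or at another time up to 24 hours before surgery. A participant allocated to an LCS arm can miss it, and the plan does not say in which group that person is analysed.
2. **Number of groups.** A split into people who did and did not work with the LCS cannot separate in-person from virtual delivery, which is the whole of Aim 3.
3. **Time.** Tied to the wearable period, the comparison stops at about the 2-week visit, although surveys continue to 3 months.

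At stake is the analysis that bears on whether the LCS works. Grouping by attendance gives up the protection of randomisation. Wording that can be read more than one way also lets an analyst choose the grouping and the time point after seeing the data and still claim to have followed the plan.

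**Working it through.** **Text against text.** There is no planned figure to reproduce on this point. Section 10 gives a sample size of 150 without power inputs.

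| Item | Sections 2 and 4 | Between-group clause in Section 19, read literally |
|---|---|---|
| Grouping | Randomised arm | Contact with the LCS |
| Groups | Three arms; LCS arms vs control, and in-person vs telehealth | Two |
| Postoperative visits | 2 weeks, 6 weeks, 3 months | 2 weeks only (1 of 3) |
| Postoperative days | About 90 | About 14 (14/90 = 16%) |

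**What an as-treated reading could do.** Only the SD of 10 comes from the documents (the PROMIS population norm in Section 6, not a planning SD). The rest is assumed:

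- 50 per arm, since the allocation ratio is not stated;
- zero true effect;
- a share p = 10% to 30% of the 100 LCS-arm participants never meet the LCS;
- those participants score D = 3 to 5 T-score points worse at follow-up regardless;
- one unadjusted comparison at one visit, on a scale where higher is worse.

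Set every randomised arm's mean to 0. Within the LCS arms, attenders then average -pD and non-attenders (1-p)D. If non-attenders are counted with the controls:

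- attender group: n1 = 100(1-p), mean -pD;
- other group: n2 = 50 + 100p, mean 100p(1-p)D / (50 + 100p);
- bias B = -pD - 100p(1-p)D / (50 + 100p);
- SE = 10 × sqrt(1/n1 + 1/n2);
- probability of rejecting at two-sided 5% = Φ(|B|/SE - 1.96) + Φ(-|B|/SE - 1.96).

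| p | D | n1 | n2 | Attenders | Others | B | SE | Rejection |
|---|---|---|---|---|---|---|---|---|
| 10% | 3 | 90 | 60 | -0.30 | +0.45 | -0.75 | 1.67 | 7.3% |
| 20% | 5 | 80 | 70 | -1.00 | +1.14 | -2.14 | 1.64 | 25.8% |
| 30% | 5 | 70 | 80 | -1.50 | +1.31 | -2.81 | 1.64 | 40.5% |

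Compared as randomised, the same population gives (1-p)(-pD) + p(1-p)D = 0 in the LCS arms and 0 in control, so there is no bias.

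**Sensitivity to the assumptions.** If non-attenders would do better (D negative), B keeps its size and changes sign. If their deficit is already fully present at baseline, it cancels in an analysis of change; only the part by which they change differently remains.

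**The case against.** The strongest reply is that this is loose drafting and not a flawed method. Section 5 defines control as the arm without the LCS, and both other arms receive it, so a split by working with the LCS is a natural shorthand for LCS arms versus control. No section says that an allocated participant who misses the session is moved to the controls. The wearable phrase may belong only to the actigraphy comparison of Aim 2, where such a limit is proper. The longitudinal part of the same sentence carries no 2-week limit.

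A reader might infer that the randomised arms are never to be compared and that the 6-week and 3-month outcomes are dropped. The documents do not support that. Section 2 sets comparisons by arm, some expressly as randomised, and the later outcomes are collected and fall under change over time. What is missing is an analysis in Section 19 that carries those comparisons out.

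The illustration also has limits. Neither the non-attendance rate nor the deficit is in the documents, and the direction of bias is unknown. Non-attendance may be uncommon: Section 9 places the LCS meeting at the baseline visit, the virtual arm need not travel, and Section 18 offers transport help. The 41% needs the worst value of both inputs and is not an expected error rate.

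All of this stands, and it narrows the point. It does not remove it. An aim states what to compare, not how, and no reading of the two-group wording gives Aim 3 an analysis.

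**Conclusion.** The point holds as a mismatch between the analysis section and the aims. Section 19 does not name randomised arm, the three-arm contrasts or arm-by-visit, and its one between-group clause, taken literally, gives a non-randomised two-group comparison at one of three postoperative visits. It should be corrected, because the clause governs the trial's main question.

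Whether the clause was meant as-treated, and whether the window was meant for all outcomes, cannot be decided from the text. The gap for Aim 3 does not depend on that. The size does: under the stated assumptions the as-treated reading produces a spurious difference of about 0.75 to 2.8 T-score points, with two-sided error of about 7% to 41% in place of 5%. These figures illustrate a risk and do not predict the trial's result. The loss of randomisation's protection under that reading does not depend on the assumed values.

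**What to change.** Keep the demographic analysis in Section 19 and replace only the between-group clause, for example with:

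> All randomised participants will be analysed in the arm to which they were randomised, regardless of LCS attendance. A mixed model for repeated measures will include arm (in-person, virtual, control), visit (2 weeks, 6 weeks, 3 months) and arm-by-visit, with contrasts of the LCS arms versus control (Aims 1 and 2) and in-person versus virtual (Aim 3).

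Then state that the wearable-period restriction applies to actigraphy outcomes only; these use the same randomised grouping over the recording period. Report any comparison by actual LCS attendance only as a labelled sensitivity analysis.

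The cost is wording: no new data, visits or participants. The as-randomised estimate may be smaller than an as-treated one. If the session does nothing for those who miss it, the estimate shrinks by the factor 1-p. For an assumed true effect of 0.5 SD, 100 LCS participants versus 50 controls and two-sided 5%, power is 82% with full attendance and 74%, 64% and 52% at 10%, 20% and 30% non-attendance. That is the price of answering the question that Hypothesis 1.1 asks.
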